## Kingdom of Bahrain:

Kingdom of Bahrain is one of the leading countries in COVID-19 outpatient treatment care. A unique outpatient clinic has been established in May 2021 to provide outpatient care for patients with positive Coronavirus. Treatment including monoclonal antibodies such as Bamlamivimab, Regen-Cov, Sotorovimab and Paxlovid™ are offered for all high-risk and close contact patients, such treatments are in line with the guidelines of the FDA.

The clinic has a dedicated call center providing different services to ease the patient treatment process and provides follow-up care. The overall aim of the clinic is to target mild to moderate high risk COVID-19 patients and provide outpatient treatment as early as possible to reduce disease progression, including hospitalization and death.

On 01 January 2022, the National Health Regulatory Authority (NHRA) approved the emergency use of Paxlovid™ for mild-moderate cases who are at high risk – identified as per WHO definition of high-risk group – of developing severe COVID-19. Since approval, Paxlovid™ has been established as the first line therapy along with Sotrovimab in the Kingdom of Bahrain.

In the EPIC-HR trial, Paxlovid™ reduced the risk of hospitalization or death by 88% compared to placebo in non-hospitalized adults with laboratory-confirmed SARS-CoV-2 infection and a risk factor for progression to severe disease, when treatment was initiated within 5 days of symptom onset. Other efficacies reported for COVID-19 therapies, include sotrovimab (ie, 85% relative reduction reported), and remdesivir (ie, 87% relative reduction reported) and molnupiravir (ie, 30% relative reduction reported). Furthermore, *in vitro* analyses, suggested that Paxlovid™ is active against the B.1.1.529 (Omicron) variant of concern (VOC).

COVID-19 has put significant pressure on the healthcare system worldwide and caused an enormous economic burden to society. While patient characteristics, healthcare resource utilization (HRU) and healthcare costs of patients hospitalized with COVID-19 have previously been described in US studies, such data are limited among non-US countries. Furthermore, while the majority of current research focuses on hospitalized COVID-19 patients, little is known about COVID-19 patients identified in an outpatient setting.

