**Table 1. Cohort Definitions**

Name	Criteria	Identification Period	Index Date	Follow Up Period
Treated patients	Patients diagnosed with COVID-19 and treated with Paxlovid™	After Paxlovid™ availability during the same dominant variant (ie, Omicron or Delta etc.) era timeframe as Cohort	Paxlovid™ prescription written date or dispense date*  If neither of the above are available, the COVID-19 diagnosis date may be used as the index date	28 -days follow up
Control group	Patients diagnosed with COVID-19 and not treated with Paxlovid™	After Paxlovid™ availability during the same dominant variant (ie, Omicron or Delta etc.) era timeframe as Cohort	Date of COVID-19 diagnosis	28 -days follow up

\*If both dates are available in the data source, the most recent date should be used as the index date for Cohort.

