**Table 3. Clinical Characteristic Variables**

Variable	Operational definition
Comorbidities	A full list of comorbidities is detailed below and according to eCRF: Distribution of patients diagnosed with each comorbid condition during the baseline and follow-up periods. Comorbid conditions will include, but are not limited to, asthma, emphysema, chronic obstructive pulmonary disease (COPD), hypertension, diabetes, obesity, cerebrovascular disease, neurological disease, chronic kidney disease, chronic liver disease, malignancy, etc.
Risk Factors for Severe COVID-19	Distribution of patients with each of the following risk factors during the baseline and follow-up periods: 

• Age <math>\geq 50</math> years

• Obesity (BMI <math>\geq 30</math>)

• Chronic kidney disease (eGFR <math>\geq 30</math> ml/min)

• Diabetes Mellitus

• Primary and Secondary Immunosuppressive disease or immunosuppressive treatment

• Cardiovascular disease (including congenital heart disease) or hypertension

• Chronic lung diseases (for example, chronic obstructive pulmonary disease, asthma [moderate-to-severe], interstitial lung disease, cystic fibrosis, and pulmonary hypertension)

• Sickle cell disease

• Neurodevelopmental disorders (for example, cerebral palsy) or other conditions that confer medical complexity (for example, genetic or metabolic syndromes and severe congenital anomalies)

• Having a medical-related technological dependence (for example, tracheostomy, gastrostomy, or positive pressure ventilation [not related to COVID-19])

Death	Distribution of patients who died on or after the enrollment date in the follow up period.

PFIZER CONFIDENTIAL

CT24-WI-GL02-RF02 4.0 Non-Interventional Study Protocol Template For Secondary Data Collection Study

15-Jun-2022

Page 17 of 41

Variable	Operational definition
Inpatient Death	Distribution of patients who died during a hospitalization in the follow-up period.

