## 9.6. Data Management

EHR data will be obtained via a retrospective review of participant charts and used to discern participant-reported symptom onset, symptom duration, and relevant laboratory findings for diagnostic criteria or other related information described in [Table 2](#) and [Table 3](#).

The unstructured data that is extracted will be put into the eCRF, will then be anonymized by the clinical research assistants and presented in the format requested by the statistician at the time of analysis.

The study will abide to European GDPR legislation for maintaining confidentiality of data.

A Data Protection Impact Assessment (DPIA) will be performed to help identify and minimize the data protection risks of the study.

The EHR database is unstructured data. Individual medical records will be extracted and anonymized and populated into an eCRF. All data will be kept securely. Details of outcome measures and adverse events will be documented in hospital healthcare records. Individual research participant data is stored in an encrypted electronic database. The study investigators will adhere to hospital protocols pertaining to healthcare record use and storage to protect the research participant's identity, a unique identification code will be assigned by the Investigator, or authorized designee, to each study participant. These will be used in lieu of the participant's name, and the unique individual study code for each participant will be used for adverse events reporting and/or other study related data to be reported. This coded form of identification, instead of the participant's name, will appear on all documents/databases and will be cross-referenced by the participants date of birth (month/year). This server has managed access and password protection. The information that this server contains is backed up every 24 hours.

Personal information will be treated as confidential, but may need to be reviewed by authorized representatives of the Sponsor (such as monitors and auditors), the Contract Research Organization, the ethics committee and the regulatory authorities. The investigators and authorized designees will ensure that the confidentiality of the participants data is preserved.

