***Kingdom of Bahrain:***

*Kingdom of Bahrain is one of the leading countries in COVID-19 outpatient treatment care. A unique outpatient clinic has been established in May 2021 to provide outpatient care for patients with positive Coronavirus. Treatment including monoclonal antibodies such as Bamlamivimab, Regen-Cov, Sotorovimab and PaxlovidTM are offered for all high-risk and close contact patients, such treatments are in line with the guidelines of the FDA.*

*The clinic has a dedicated call center providing different services to ease the patient treatment process and provides follow-up care. The overall aim of the clinic is to target mild to moderate high risk COVID-19 patients and provide outpatient treatment as early as possible to reduce disease progression, including hospitalization and death.*

*On 01 January 2022, the National Health Regulatory Authority (NHRA) approved the emergency use of Paxlovid™ for mild-moderate cases who are at high risk – identified as per WHO definition of high-risk group – of developing severe COVID-19. Since approval, Paxlovid™ has been established as the first line therapy along with Sotrovimab in the Kingdom of Bahrain.*

*In the EPIC-HR trial, Paxlovid™ reduced the risk of hospitalization or death by 88% compared to placebo in non-hospitalized adults with laboratory-confirmed SARS-CoV-2 infection and a risk factor for progression to severe disease, when treatment was initiated within 5 days of symptom onset.Error! Reference source not found.Error! Reference source not found. Other efficacies reported for COVID-19 therapies, include sotrovimab (ie, 85% relative reduction reported),Error! Reference source not found.Error! Reference source not found. and remdesivir (ie, 87% relative reduction reported)Error! Reference source not found.Error! Reference source not found. and molnupiravir (ie, 30% relative reduction reported).Error! Reference source not found.Error! Reference source not found. Furthermore, in vitro analyses, suggested that Paxlovid™ is active against the B.1.1.529 (Omicron) variant of concern (VOC).Error! Reference source not found.*

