## 1.1 STUDY DESIGN

This study is a retrospective cohort study examining COVID-19 patients who were treated with Paxlovid. It will also include a control group of COVID-19 patients who were offered, but refused, Paxlovid. It will involve a secondary data analysis of patient data from the ISeha electronic medical records.

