Non-invasive Ventilation Usage	Non-invasive ventilation usage during COVID-related hospitalizations in the baseline and follow-up periods (excluding within 24 hours of Paxlovid initiation)
High-flow Nasal Cannula Usage	High-flow nasal cannula usage during COVID-related hospitalizations in the baseline and follow-up periods (excluding within 24 hours of Paxlovid initiation)
Hospital Discharge Status	Patient discharge status for COVID-related hospitalizations during the baseline and follow-up periods (excluding within 24 hours of Paxlovid initiation)

PFIZER CONFIDENTIAL

CT24-WI-GL03-RF03 2.0 *Non-Interventional Statistical Analysis Plan For Secondary Data Collection*  
*Study 01-Jun-2020*  
 Page 11 of 22

Time from COVID-19 Test to Paxlovid Treatment	Time from the earliest COVID-19 test in the baseline period to the earliest date of Paxlovid prescription written date AND dispense date.
COVID-19 Lab Tests with Positive Result	COVID-19 lab test with a positive result during the baseline and follow-up periods.
COVID-19 Lab Test with Variant Type	When available, COVID-19 variant of concern (VOC) during the baseline period.
Treatment drugs being receiving at the index date	-Use Positive test as the INDEX Date and record use of any medicine listed in the potential DDI/Contraindications section of the EUA/:Label
Monoclonal Antibody Usage	Monoclonal antibody usage during the baseline and follow-up periods. Monoclonal antibody usage will include tocilizumab and bamlanivimab/etesevimab. (Yes/No)
Antiviral Usage	Antiviral therapy usage during the baseline and follow-up periods. Antiviral therapy usage will include remdesivir, nirmatrelvir/ritonavir (paxlovid) and molnupravir. (Yes/No)
Steroid therapy	Steroid therapy during admission (Yes/No)

PFIZER CONFIDENTIAL

CT24-WI-GL03-RF03 2.0 *Non-Interventional Statistical Analysis Plan For Secondary Data Collection*  
*Study 01-Jun-2020*  
 Page 12 of 22

WHO guidelines on COVID-19 therapeutics include the following groups

- **High risk:** people who are immunosuppressed; estimated hospitalization rate of 6%.
- **Moderate risk:** >65 years of age, conditions like obesity, diabetes and/or chronic conditions including chronic obstructive pulmonary disease, kidney or liver disease, cancer, with disabilities, and with comorbidities of chronic disease; estimated hospitalization rate of 3%.
- **Low risk:** those who are not in the high or moderate risk categories; low risk of hospitalization (0.5%) – most people are low risk.

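### The monoclonal-antibody variable does not name sotrovimab or Regen-Cov, and the SAP Table 7 shell pools monoclonals with Paxlovid, so other therapy may be miscoded and is hidden in the Paxlovid group

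*SAP*

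**What the plan says.** - **Variable.** SAP Table 4 records monoclonal use as Yes/No over the baseline and follow-up periods: "Monoclonal antibody usage will include tocilizumab and bamlanivimab/etesevimab". Protocol Table 5 names the same products. The antiviral variable next to it names remdesivir, Paxlovid and molnupiravir.
- **Local practice.** Protocol Section 7, under Kingdom of Bahrain, says: "Treatment including monoclonal antibodies such as Bamlamivimab, Regen-Cov, Sotorovimab and Paxlovid™ are offered for all high-risk and close contact patients". It adds: "Since approval, Paxlovid™ has been established as the first line therapy along with Sotrovimab in the Kingdom of Bahrain". The SAP introduction repeats this: "Paxlovid™ has been established as the first line therapy along with Sotrovimab in the Kingdom of Bahrain".
- **Control group.** Protocol Table 1 defines it as "Patients diagnosed with COVID-19 and not treated with Paxlovid™". SAP 1.1 says: "It will also include a control group of COVID-19 patients who were offered, but refused, Paxlovid". Neither definition mentions other COVID-19 therapy.
- **Reporting.** SAP 7.2.3 commits to descriptive statistics for every variable. The SAP Table 7 shell has four medication rows: antibiotics, antivirals, antithrombotics and anti-inflammatories. Monoclonals appear only inside the antiviral row, together with Paxlovid. Each row has a p-value and an effect size. The protocol's sample Table 8 pools in the same way.

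**The concern.** The study compares hospitalisation and other outcomes between Paxlovid patients and controls, with tests, 95% confidence intervals and effect sizes. To read that comparison, one needs to know what other COVID-19 therapy each group received. Two features of the plan get in the way, and they are independent of each other.

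First, the list that tells an abstractor what counts as monoclonal use leaves out two of the three monoclonals named in the documents' account of the clinic. One of the two is the product described as first line along with Paxlovid. Second, even if the coding is right, the only results row that mentions monoclonals mixes them with the drug that defines the treated group.

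At stake is correct recording and reading of treatment patterns, which are part of the study's stated aim. Protocol Section 9.9 claims association only, so this is not a challenge to a causal claim.

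**Working it through.** The documents give no figure on this point, so there is nothing to reproduce. The check compares passages, followed by two short illustrations.

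**1. Products named in the background against the variables**

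| Product | Clinic background | Monoclonal variable | Antiviral variable |
|---|---|---|---|
| Bamlanivimab | named | named (with etesevimab) | not named |
| Regen-Cov | named | not named | not named |
| Sotrovimab | named; first line along with Paxlovid | not named | not named |
| Tocilizumab | not named | named | not named |

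One of the clinic's three monoclonals is in the list. The antiviral variable does not pick up the other two.

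**2. Is the list closed?** Protocol Table 3 shows how the protocol marks an open list: "Comorbid conditions will include, but are not limited to, asthma, emphysema". The monoclonal sentence lacks that qualifier, so an abstractor could treat it as complete and code a sotrovimab or Regen-Cov recipient as No. This is a possible reading, not a certain one (see the objection). It matters because the source is free text that people will code: "The EHR database is unstructured data".

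**3. The pooled Table 7 row.** Every patient in the Paxlovid group had Paxlovid, so that cell is 100% whether none or all of them also had a monoclonal. Take about 3000 Paxlovid patients and 1000 controls (SAP, Study population), and let s be the assumed share of controls with any non-Paxlovid antiviral or monoclonal. The 2×2 table is 3000/0 against 1000s/1000(1−s), which gives

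V = √[3(1−s)/(3+s)].

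| s (assumed) | Cramer's V |
|---|---|
| 0% | 1.00 |
| 10% | √(2.70/3.10) = 0.93 |
| 25% | √(2.25/3.25) = 0.83 |
| 50% | √(1.50/3.50) = 0.65 |

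All four lie above the SAP's 0.6 mark for a large effect. None depends on co-treatment in the Paxlovid group. The result reflects how the groups were defined. These are the unmatched group sizes.

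**4. Could other therapy move the outcome contrast?** This is illustration only, because the shares are assumptions. Inputs from the documents are the 3% hospitalisation rate for WHO moderate risk and the reported reductions of 88% (Paxlovid) and 85% (sotrovimab). Effects are assumed to multiply. With a share f given sotrovimab, control risk = 3% × (1 − 0.85f). Paxlovid-group risk = 3% × 0.12 = 0.36%, times (1 − 0.85f) if that group is co-treated.

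| Assumed sotrovimab use | Control risk | Paxlovid-group risk | Difference (points) |
|---|---|---|---|
| none | 3.00% | 0.36% | 2.64 |
| 10% of controls | 2.745% | 0.36% | 2.39 |
| 25% of controls | 2.363% | 0.36% | 2.00 |
| 50% of controls | 1.725% | 0.36% | 1.37 |
| 25% of both groups | 2.363% | 0.284% | 2.08 |
| 25% of Paxlovid group only | 3.00% | 0.284% | 2.72 |

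With use in controls only, the relative reduction goes from 88.0% to 86.9%, 84.8% and 79.1%. With equal use in both groups it stays at 88%. If sotrovimab had no effect in this cohort, the difference stays at 2.64. The direction is therefore not fixed, and at low shares the shift is small. The 3% is for hospitalisation and the 88% for hospitalisation or death, so the mix is approximate.

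**The case against.** The strongest reply is that the list is not closed. The variable is headed by the drug class, its wording does not say *only*, and the Table 7 row uses the class term for COVID-19 monoclonals, which would cover both missing products. The contrast with the open-list wording in protocol Table 3 is weak evidence, because the SAP's version of that comorbidity row drops the qualifier and ends in *etc.* The commitment in SAP 7.2.3 can also be read as already requiring the monoclonal variable to be reported, which would make the missing row a formatting gap. The work is called exploratory, hypotheses are not applicable, and variables are extracted only if available.

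Much of this stands. Undercounting is conditional on how the list is applied, and the point should claim no more than that. But the ambiguity is itself a reason to name the products, since two abstractors could code the same record differently. The promise in SAP 7.2.3 does not repair the shell: as written, a programmer would produce a row that cannot inform.

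A reader might infer that Table 7 cannot show any other therapy behind the comparison. That goes too far. Controls had no Paxlovid, so in their column the pooled row shows the share with non-Paxlovid antivirals or monoclonals, as far as these were abstracted. What it does not show is which product. The blind spot is the Paxlovid column.

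**Conclusion.** The point holds in two parts. The variable in both documents does not name two products from the documents' own account of local treatment, one of them called first line along with Paxlovid; if coded by the stated list, their users can be recorded as No. The Table 7 row is 100% in the Paxlovid group by construction, so it hides other therapy there, and its p-value and effect size carry no information about it. The second part does not depend on how the list is read.

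The size and direction of any effect on the outcome comparison are unknown, because the documents give no count of sotrovimab or Regen-Cov users in either group. The risk differences above rest on assumed shares and show only that the shift could go either way.

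Two stronger conclusions are tempting and unsupported. One is that controls were widely given sotrovimab and the contrast is therefore diluted; nothing in the documents says so. The other is that other COVID-19 therapy should be in the propensity-score list. Therapy given after diagnosis is post-baseline, and matching on it would condition on later treatment, so its absence from that list is not a defect.

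This should be corrected before abstraction and programming, but it does not threaten the study's main descriptive aim.

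**What to change.** 1. Add sotrovimab and Regen-Cov to the Monoclonal Antibody Usage variable in protocol Table 5 and SAP Table 4, and record product and date where available.
2. Split the pooled row of the SAP Table 7 shell into three rows, each by group: Paxlovid, other antivirals, and monoclonal antibodies. The shell then matches the separate variables in SAP Table 4 and the commitment in SAP 7.2.3.

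The cost is slightly more abstraction, from records that are already under review, and two extra table rows. The group definitions, the matching and the main comparison need no change on this account.

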## **9. RESEARCH METHODS**

### **9.1. Study Design**

This will be a retrospective observational cohort study of patients diagnosed with COVID-19 in the Kingdom of Bahrain. Treated patients are defined as those have been prescribed nirmatrelvir, ritonavir and managed in the outpatient setting (eg, receiving medical treatment without being admitted to a hospital for COVID-19) while control group is those not treated with nirmatrelvir, ritonavir. Data will be from the *I-Seha electronic medical records* and descriptive analyses will be conducted for these two cohorts and will compare healthcare resource use in patients treated with nirmatrelvir, ritonavir and those not treated with nirmatrelvir, ritonavir.

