### 9.2.2. Exclusion Criteria

**There are no exclusion criteria for this study.**

## 9.3 Variables

The following variables are used to obtain comprehensive descriptive results.

1. Demographics
2. Date of symptoms
3. Viral variant analysis where available (type of viral variant ie, omicron, delta etc.)
4. PCR date along with CT Value

5. Co-morbidities and
6. BMI if  $\geq 30$
7. Symptoms at presentation
8. COVID 19 vaccine status (NB 92% of population has been vaccinated -with at least one dose of COVID 19 vaccine- in Bahrain)
9. Hospital admission
10. Follow up looking at compliance and reason of non-compliance
11. Day 5,7, 21 and 28 symptoms for COVID-19 patients who receive and HRU limited to admission (ICU, ward, need for oxygen therapy) or death
12. Date of symptoms resolution if applicable

**Table 2** Table 2 below depicts the patient demographics that will be accessed during the baseline and follow-up periods. The baseline period is defined as one year before the index date. Comorbidities (full list in [Table 6](#)) and maintenance medication usage for chronic conditions (eg, statins, antihypertensives, etc.) will be described during the baseline period and follow-up periods and are listed in [Table 3](#).

Risk factors for severe COVID-19, intensive care unit (ICU) usage, invasive mechanical ventilation (IMV) usage, supplemental oxygen use, non-invasive ventilation, and high-flow nasal cannula usage are depicted in [Table 5](#) and will be extracted from the *I-Seha* national electronic health record database.

Where applicable, emerging treatment patterns may be assessed as the time from symptom onset to COVID-19 diagnosis, time from symptom onset to treatment initiation, and the time from COVID-19 diagnosis to treatment initiation as illustrated in [Table 5](#).

10Nov23 WHO recommendations for Paxlovid treatments to define: 1. COVID-19 patients who meet the WHO criteria for “strongly recommended” 2. COVID-19 patients who meet the WHO criteria for “conditionally recommended”, and 3. COVID patients who are not falling into categories 1 or 2 will be used.

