Antiviral Usage	Patients with antiviral therapy usage during the baseline and follow-up periods. Antiviral therapy usage will include remdesivir, nirmatrelvir/ritonavir (Paxlovid™) and molnupiravir.
Steroid therapy	Patients with steroid therapy during admission

PFIZER CONFIDENTIAL

CT24-WI-GL02-RF02 4.0 Non-Interventional Study Protocol Template For Secondary Data Collection Study

15-Jun-2022

Page 19 of 41

Variable	Operational definition
Treatment drugs being receiving at the Index date	Use Positive test as the INDEX Date and record use of any medicine listed in the potential DDI/Contraindications section of the EUA/Label

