**Table 1: Patient Demographic Variables**

Variable	Operational definition
Group	Received Paxlovid or did not receive Paxlovid
Age	Age will be defined as of the date of COVID-19 diagnosis using a PCR test and will be used to assign patients to age groups: 18-29, 30-49, 50-64, 65-74, $\geq 75$ years and unknown/missing age
Sex	Female, male and unknown/missing sex patients
Nationality	Nationality of the patient (Bahrain, other Middle East and North Africa, India, Pakistan, South East Asia, Caucasian)
Enrollment Date Place of Service (POS)	Type of outpatient encounter during the enrollment date (e.g., office visit, emergency room (ER), outpatient hospital, other, etc.)
Enrollment Date	Date (defined as MM/YYYY) of the enrollment date specified
Specialty of Provider at enrollment Date	Provider specialties present during the enrollment date. Patients with no provider specialty recorded will be included in an “Unknown/missing specialty” category
COVID-19 Symptom Onset Date	Date of symptom onset prior to presentation to healthcare facility

PFIZER CONFIDENTIAL

CT24-WI-GL03-RF03 2.0 *Non-Interventional Statistical Analysis Plan For Secondary Data Collection*  
*Study 01-Jun-2020*  
 Page 8 of 22

Time to COVID-19 Symptom Resolution	Time from onset of COVID-19 symptoms to resolution of symptoms
Date of COVID-19 Vaccination	Date of each COVID-19 vaccination received. Note: patient-specific vaccination history may require more than 6-months pre-index time period.
Date of Paxlovid prescription written and/or fill history (e.g., prescription claim)	Date of Paxlovid prescription written or fill history. Note: if both dates are available within the database, use the most recent date provided.

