**Table 7: Descriptive statistics for outcome variables**

Outcome Variables	Group		P-value	Effect size
	Paxlovid	Control		
Hospitalizations, % (n)				
Number of hospitalizations per patient, mean (SD)				
Number of hospitalizations per patient among patients with readmissions, % (n)				
Time to first outpatient encounter, mean (SD)				
ICU Admission, % (n)				
Hospital Length of Stay, mean (SD)				
ICU/Non-ICU LOS, mean (SD)				
IMV/No IMV LOS, mean (SD)				
Treatment				
IMV Usage, % (n)				
Supplemental Oxygen Usage, % (n)				
Non-invasive Ventilation Usage, % (n)				
High-flow Nasal Cannula Usage, % (n)				
Hospital Discharge Status				
Went home, % (n)				
Transfer to skilled nursing facility, % (n)				

PFIZER CONFIDENTIAL

CT24-WI-GL03-RF03 2.0 *Non-Interventional Statistical Analysis Plan For Secondary Data Collection Study* 01-Jun-2020

Page 20 of 22

Transfer to other healthcare facility, % (n)				
Transfer to other long-term care facility, % (n)				
Transfer to hospice, % (n)				
Death, % (n)				
Medication Usage, % (n)				
Antibiotic, % (n)				
Antiviral (incl. Paxlovid, COVID-19 monoclonal antibodies), % (n)				
Antithrombotic, % (n)				
Anti-inflammatory (incl. steroids), % (n)				

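### The antiviral-use row counts Paxlovid, the drug that defines the groups, so its between-group test is largely circular and it cannot show other antivirals in treated patients

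*SAP*

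**What the plan says.** SAP Table 4 lists Antiviral Usage among the disease outcome variables. Its window is "Antiviral therapy usage during the baseline and follow-up periods", and its content is "Antiviral therapy usage will include remdesivir, nirmatrelvir/ritonavir (paxlovid) and molnupravir. (Yes/No"). Protocol Table 5 pools the same three drugs: "Antiviral therapy usage will include remdesivir, nirmatrelvir/ritonavir (Paxlovid™) and molnupiravir". In both tables monoclonal antibody usage is a separate variable.

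The SAP Table 7 shell, under Medication Usage, has one row, "Antiviral (incl. Paxlovid, COVID-19 monoclonal antibodies), % (n"), with columns for Paxlovid, Control, P-value and Effect size. It has no row for an individual antiviral and none for antibodies alone.

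The groups are defined by the same drug. The SAP Table 1 group variable is "Received Paxlovid or did not receive Paxlovid". Protocol section 9.1 states: "Treated patients are defined as those have been prescribed nirmatrelvir, ritonavir and managed in the outpatient setting". Protocol Table 1 sets the treated index date at the "Paxlovid™ prescription written date or dispense date", with the diagnosis date as fallback. Protocol section 9.3 adds: "The baseline period is defined as one year before the index date".

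SAP section 1.13 applies proportions, chi-square or Fisher tests to categorical variables at alpha 0.05, reports Cramer's V, and labels 0.6 as Large.

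**The concern.** An outcome that contains the exposure cannot be compared informatively between exposed and unexposed patients. A treated patient scores Yes by being in the treated group, so a treated patient later given remdesivir looks the same as one who took only Paxlovid. A control scoring Yes could have had remdesivir, molnupiravir, a later Paxlovid course or, in Table 7, an antibody.

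The study sets out to compare healthcare resource use and outcomes between the groups (Protocol section 9.1; SAP objective (iv)). Knowing what other COVID-19 therapy each group received helps in reading that contrast. As drafted, the row would instead print a very small p-value and a large effect size, under an outcome heading, for a difference that the cohort definition creates.

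**Working it through.** The documents state no rate or power for antiviral use, so there is no planned figure to reproduce.

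**Inputs.** Treated about 3000 and controls about 1000 (SAP, Study population). Treated Yes = 100%, from the group definition. Control rate q is an assumption, shown over a range.

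**Cramer's V for the row.** The 2×2 table is 3000 Yes and 0 No in the treated group, 1000q Yes and 1000(1 − q) No in controls. With Pearson chi-square and no continuity correction, V² = chi²/4000 = 3(1 − q)/(3 + q).

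| Assumed q | Difference (points) | V |
|---|---|---|
| 0% | 100 | 1.00 |
| 2% | 98 | 0.99 |
| 5% | 95 | 0.97 |
| 10% | 90 | 0.93 |
| 20% | 80 | 0.87 |
| 50% | 50 | 0.65 |

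The computed p-value was zero to machine precision in every line.

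**Where the Large label stops.** Setting V = 0.6 gives 0.36(3 + q) = 3(1 − q), so 3.36q = 1.92 and q = 0.571. At q = 60%, V = √(1.2/3.6) = 0.58. The threshold depends on the 3:1 group sizes. The SAP also mentions propensity-score matching; if that produced 1:1 groups (an assumption), V² = (1 − q)/(1 + q) and the threshold would be q = 0.64/1.36 = 0.47.

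**Blindness in the treated group.** If 0%, 1% or 5% of treated patients later receive remdesivir or molnupiravir, the treated count is 3000 of 3000 each time.

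**Ambiguity in controls.** Twenty Yes among 1000 controls gives 2% and V = 0.987, whether all 20 are Paxlovid, none are, or any mix.

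**If usage means taken rather than prescribed.** The protocol plans to look at compliance, so treated use might fall short of 100%. At an assumed 90 to 99% intake, with 2% in controls, V is 0.82 to 0.97.

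**With Paxlovid taken out (rates assumed).**
- 0.5% treated against 2% control: difference −1.5 points; standard error √(0.005 × 0.995/3000 + 0.02 × 0.98/1000) = 0.0046; 95% CI −2.4 to −0.6; V = 0.07.
- 1% against 1%: difference 0; 95% CI −0.7 to 0.7; V = 0.

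The row then responds to actual use of the other drugs.

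**The case against.** The best defence is that little rests on this row. Antiviral use is not named in the protocol objectives or among the examples in SAP objective (iv). Section 9.3 of the protocol limits follow-up resource use to admission, oxygen need and death. The SAP has no hypotheses or decision rules and calls its testing exploratory. The row is openly labelled as including Paxlovid, so a reader who sees 100% is unlikely to take it as a finding. All of this stands and keeps the severity low. It does not make the row informative, and the shell still attaches a test to it.

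Four stronger readings are tempting, and the documents do not support them:

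- *A refuser who later starts Paxlovid is invisible.* If that patient stays in the control group, the flag changes from No to Yes. The event is counted but not identified, because the drugs are pooled. SAP Table 1 also extracts the Paxlovid prescription or fill date, so the event may be recoverable, although no table reports it. Read literally, the group variable could instead move the patient into the Paxlovid group; the SAP gives no rule.
- *The effect is Large whatever other drugs are used.* It is not once control use passes about 57%. Both documents describe sotrovimab as first line alongside Paxlovid, and Table 7 counts antibodies, so control use could be well above a few percent.
- *This is a follow-up outcome.* The definition names baseline and follow-up together, so antiviral use in the year before index could also score Yes.
- *Drug-level data are collected and then merged.* The definition names the drugs but specifies Yes/No, and no eCRF layout is given. Either is possible.

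**Conclusion.** The point holds for the treated group. Antiviral Usage contains the drug that defines that group, so treated patients are essentially 100% Yes, the comparison mostly restates the grouping, and added remdesivir or molnupiravir cannot be seen. No passage leaves out the index course. In controls the weakness is narrower: a Yes does not say which drug.

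On size, V is 1.00 to 0.65 for an assumed control rate of 0 to 50% at the planned 3:1 sizes. This rests on reading usage as prescribed or dispensed and on counting the index course, as the Table 7 label indicates. Lower intake softens the figure without changing the conclusion.

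Severity is low: one secondary row is uninformative as drafted, and no main contrast is invalidated.

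**What to change.** - In SAP Tables 4 and 7, report remdesivir and molnupiravir as separate rows by group, with baseline and follow-up shown separately. State the follow-up length used, since the protocol gives 28 days and SAP objectives (iii) and (iv) give five.
- Exclude the index Paxlovid course from the treated group's antiviral rows.
- Give monoclonal antibodies their own Table 7 row, in line with their separate definition in SAP Table 4. Deleting only the mention of Paxlovid would leave them merged.
- Add a descriptive, untested row for controls with a later Paxlovid record, using the date field in SAP Table 1, and state which analysis group those patients belong to.
- Drop the p-value and effect size for any row whose result the group definition fixes.

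The cost is a few table rows and some SAP wording, plus a check that the eCRF records antivirals by drug. If it holds only the pooled flag, that field has to be split at abstraction.
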